The University of Texas Medical Branch at Galveston

Research Protocol # 21-0045

Title: Subcuticular Absorbable Staples Versus Conventional Skin Closure in Women Undergoing Cesarean Delivery: A Randomized Control Trial

Prepared by:

[name] (Principal Investigator)
The University of Texas Medical Branch
[name]
[name]

[name] (Faculty Sponsor)
The University of Texas Medical Branch
[name]
[name]

Sponsor: Cooper Surgical

Email: [contact] Direct: [name] – [contact]

1. Introduction and Purpose:

Cesarean delivery is the most common major operating room surgery, with yearly rates increasing worldwide. Despite the high numbers of cesareans being performed, scientific evidence behind which surgical techniques are best remains uncertain. Consequently, there is significant interest in optimizing surgical techniques. Our objective is to determine if subcuticular absorbable staples improve operative time and wound cosmetics.

2. Background:

Cesarean delivery is the most common surgical procedure in the USA. Despite a concerted effort to decrease the cesarean delivery rate, it continues to hover around 30%. There is clear interest in optimizing surgical techniques. The optimal skin closure technique after cesarean delivery remains unknown. The effect of different skin closure techniques, such as suture versus staple closure, on decreasing wound morbidity and closure time, as well as improving aesthetics remains unclear. Supporting arguments for the use of either closure types remain controversial.

Randomized controlled trials comparing surgical steel staples to subcuticular sutures found no difference in wound cosmesis.[1-3] However, some studies reported increase in wound infection rates in patients who received steel staples. There are conflicting results regarding postoperative pain; one study concluded less pain with suture techniques [1], while another [3] showed the opposite. While steel staple closure is easier to perform and master than subcuticular suture closure, it requires an additional clinic visit for removal of the staples. Staple closure can also lead to the misdiagnosis of a wound infection, as it is associated with induration and erythema.

The recent introduction of absorbable subcuticular staples combines the best of both approaches. Animal studies showed absorbable subcuticular staple closure leads to less histological inflammation [4] and less wound infections compared to steel staples [5]. Clinical trials in cesarean are lacking. In a retrospective cohort study [6], this new device led to less in-hospital analgesic use compared to steel staples. Another study [7] showed that women who had skin incision closure with absorbable subcuticular staples had lower rates of wound complication compared to steel staples but similar to absorbable sutures. Both studies concluded that level 1 evidence trial is needed to further support and verify these results.

3. Concise Summary of Project:

This will be an open-label randomized controlled clinical trial. Women undergoing cesarean delivery will be randomized to have either standard wound closure with Monocryl suture or absorbable subcuticular staples placed by INSORB skin stapling device. The INSORB under the skin stapling device is FDA approved but not currently used as standard of care at UTMB. We will exclude women with intraamniotic infection, immunosuppression, active skin infection, those unlikely to be followed-up after delivery, or unable to provide consent.

Potentially eligible subjects will be informed by the obstetrical team about the study and asked for permission to contact the study personnel. Written informed consent will be obtained by person-to-person contact. The research staff will be responsible for the informed consent.

Subjects who agree to participate in the study will be randomized to one of the two groups below in a 1/1 allocation:

- Suture wound closure: absorbable sutures for closure of cesarean skin incision using Monocryl manufactured by Ethicon.
- Absorbable staple wound closure: staples will be applied as per the manufacturer's instructions (Appendix A) intraoperatively using INSORB device manufactured by Cooper Surgical.

The remainder of the subjects' care, including wound care, will be similar for both arms and will follow current standard clinical practice at the University of Texas Medical Branch (UTMB). The study period will be between 2021 and 2023. The number of subjects to be studied at UTMB will be 352. A subject will be withdrawn from the study if she wishes to discontinue participation.

4. Inclusion Criteria:

- 18-50 years of age.
- Women ≥ 24 weeks viable gestation.
- Will be undergoing cesarean delivery.

5. Exclusion Criteria:

- Patient unwilling or unable to provide consent.
- No or very limited prenatal care or a non-resident patient who is unlikely to follow-up after delivery.
- Immunosuppressed subjects: i.e., taking systemic immunosuppressant or steroids (e.g. transplant subjects; not including steroids for lung maturity), HIV with CD4 <200, or other.

- Decision not to have skin closure (e.g. secondary wound closure, mesh closure).
- Current skin infection.
- Coagulopathy.
- High likelihood of additional surgical procedure beyond planned cesarean with our without tubal ligation (e.g. scheduled hysterectomy, unplanned tubal ligation, bowel or adnexal surgery).
- Incarcerated individuals.
- Intraamniotic infection.
- Subjects participating on other treatment trials or studies that would interfere with the current study's primary outcome.

6. Study Procedures:

6.1 Screening Recruitment and Consenting:

Under the direction of the PI, trained research staff will be available 24/7 to screen and consent subjects. Subjects will be enrolled at the time of admission to labor and delivery (L&D) for delivery or thereafter when decision for cesarean section is made. Medical records of all potential subjects will be reviewed and those who satisfy eligibility criteria will be approached and written informed consent obtained. Potential subjects with whom there is no treating relationship, the permission of the treating provider will be obtained prior to approaching subjects to participate in the study. A screening log will be used to track all subjects approached for the study. Women will be randomized in the operating room when the decision is made to proceed with skin closure and they continue to be eligible.

Recruitment: We will offer the trial to all pregnant subjects admitted to L&D and who meet our eligibility criteria. Whenever practical and feasible, information about our research project will be made available to subjects prior to labor. Once the inclusion criteria for our study are met, the clinical team will inform the subject about the study and ask her authorization to contact one of the study personnel. We will not consent subjects who appear not to be able to evaluate their options (such as recent intravenous narcotics). This strategy is currently followed in other approved OB/GYN studies with similar recruitment timing and has been well received among participants without concerns or complaints. Once the inclusion criteria for our study are met, the clinical team will inform the subject about the study and ask her authorization to contact one of the study personnel.

Consenting process: Written consent will be obtained by direct person-to-person contact. The research staff will be responsible for the informed consent. Written consent will be obtained. The consent form will be thoroughly reviewed with the

subjects prior to signing. Details of participation as well as risks and benefits will be discussed with the patient. Questions will be invited and just prior to signing, the research staff will ask questions of the subject to ensure her complete understanding of the study and her voluntary willing participation. Subjects will be informed that their decision about participating in the study will in no way affect the care they will receive. Research team members will be available for any further discussion or questions/concerns expressed by the patient. For non-English speaking subjects, informed consent will be provided in their primary language (Spanish). A certified translator will review the consent with them which will be provided in their own language .The research data collected will not be used for clinical diagnosis or treatment purposes. Subjects will be reassured that participation in the study is voluntary and will not interfere with diagnose or treatment of her condition. The subjects will receive the same care and expertise as any other patient treated in our unit.

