6.7. Secondary Outcomes

- Need of in hospital analgesics
- Composite wound complication.
 - Defined as presence of any of the following within 30 days from surgery: Wound infection: Presence of either superficial or deep incisional surgical site infections described as cellulitis/erythema and induration around the incision or purulent discharge from the incision site, with or without fever, such as necrotizing fasciitis (diagnosed based on necrotizing wound infection). Wound hematoma, seroma, or breakdown alone.

- Endometritis, wound infection (including necrotizing fasciitis), other infections including abscess, septic thrombosis, pneumonia, pyelonephritis and breast infection.
- Maternal Death.
- Puerperal fever: temperature >100.4°F after first 24 hours or ≥101°F any time.
- Postpartum antibiotic use.
- Wound hematoma or seroma.
- Wound dehiscence.
- Use of resources: hospital stay, postpartum clinic or emergency room visit within 30 days of delivery, need for imaging or other invasive procedures.
- Adverse events: allergic reactions (anaphylaxis, angioedema, skin rashes including Stevens Johnson and Toxic Epidermal Necrolysis).
- Bluebelle Wound Healing Questionnaire for assessment of surgical-site infection/wound complications in closed primary wounds during wound check visit on POD 5-10 days standard visit, which will be completed by the patient
- Analog pain scale ranging from 0-10 on postoperative days 1 to 3 as well as at wound check visit, this is a standard question that nurses as during the post partum period while in the hospital and clinic/nursing visits. The numerical score will be recorded from the patient's chart.
- Wound cosmesis on POD 5-10 visit postpartum visits: A digital photograph of the incision will be obtained on wound check visit POD 5-10 days and 4-6 weeks postoperative. Each photograph will be evaluated according to objective criteria (width, elevation, color, marks, and general appearance) by independent blinded research staff using the Stony Brook Scar Evaluation Scale
- Satisfaction a questionnaire POD 2-3 (before discharge) and at wound check visit (Appendix B).

7. Sources of Research Material:

Electronic Medical chart/records, questionnaires, photographs.

8. Potential Risks:

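### Nothing in the plan keeps women from knowing their closure, so the patient-reported secondary outcomes are open to an expectation bias that a small change could reduce

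*Combined protocol and SAP*

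**What the plan says.** - **Masking.** Section 3: "This will be an open-label randomized controlled clinical trial". The plan gives no reason for leaving participants unmasked and no measure to withhold the allocation from them. The one masked element is cosmesis, which section 6.7 has rated from photographs "by independent blinded research staff using the Stony Brook Scar Evaluation Scale".
- **Timing of allocation.** Section 6.1: "Women will be randomized in the operating room when the decision is made to proceed with skin closure and they continue to be eligible". Consent comes earlier, and at that point "Details of participation as well as risks and benefits will be discussed with the patient".
- **The two closures.** Section 3 describes the stapler thus: "The INSORB under the skin stapling device is FDA approved but not currently used as standard of care at UTMB". The comparator is "absorbable sutures for closure of cesarean skin incision using Monocryl manufactured by Ethicon". Section 3 also says that the rest of care, wound care included, is similar in both arms.
- **Patient-reported outcomes.** Section 6.7 lists, all as secondary outcomes, the Bluebelle questionnaire at the postoperative day 5-10 visit ("which will be completed by the patient"), a 0-10 pain score on days 1 to 3 and at the wound check, and a satisfaction questionnaire before discharge and at the wound check.
- **Direction of expectation.** Section 11 names less pain and improved satisfaction among the potential benefits of the stapler.
- **Primary outcome.** Operating-room case time in minutes, which is not patient-reported.

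**The concern.** The surgeon cannot be masked to the closure; the woman possibly can. She does not know her arm when she consents, because it has not yet been assigned. Afterwards nothing in the plan stops her from learning it before she scores her pain, her wound and her satisfaction. She has agreed to a comparison of a device new to the site with its usual suture, and the potential benefits that the protocol lists for that device include the things she is then asked to rate.

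If knowing the arm moves those ratings, the difference between arms combines a real effect with a reporting effect, and no later analysis can separate them. Masking the photograph raters does not help here, because it protects only the cosmesis score. At stake is what the trial can say about pain, satisfaction and patient-reported wound healing.

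**Working it through.** **1. The plan's own figure.** Section 12 gives a suture-arm mean of 55.46 min, SD 13.63 and a 5-minute reduction, with two-sided alpha 0.05 and 90% power.

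- Effect size d = 5/13.63 = 0.36684.
- Noncentrality = d × √(n/2). At n = 158 per arm this is 0.36684 × √79 = 3.2605, on 314 degrees of freedom, with critical t = 1.96755.
- Power from the noncentral t is 0.9016 at 158 per arm and 0.8998 at 157. The stated 316 is reproduced.
- 316/(1 − 0.10) = 351.1, rounded up to 352. This is reproduced too.

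These figures rest on operating-room time alone, so masking participants changes none of them.

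**2. What difference reaches significance on a patient-reported score.** For any continuous score with 158 per arm, P<0.05 needs an observed difference of at least 1.96755 × √(2/158) = 0.221 SD.

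**3. False-positive probability under a pure expectation shift.** The documents give no SD for pain and no size for an expectation effect, so both are assumptions. Suppose the closures have no true effect on pain, but awareness moves the mean of one arm by b points. The rejection probability is that of the two-sided noncentral t with noncentrality (b/SD) × √(n/2), at n = 158 per arm.

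| Assumed shift b | Assumed SD | b/SD | Noncentrality | P(p<0.05) |
|---|---|---|---|---|
| 0 | any | 0 | 0 | 0.05 |
| 0.3 | 2.5 | 0.12 | 1.067 | 0.186 |
| 0.3 | 2.0 | 0.15 | 1.333 | 0.265 |
| 0.5 | 2.5 | 0.20 | 1.778 | 0.426 |
| 0.5 | 2.0 | 0.25 | 2.222 | 0.601 |

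In SD units, a shift of 0.05 SD gives 0.073 and one of 0.10 SD gives 0.144. With all 176 per arm contributing, a shift of 0.10 SD gives 0.155 and one of 0.20 SD gives 0.465, against 0.426 at 158. The result depends far more on the assumed shift than on the number analysed.

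**4. Whether masking is plausible on the documents' own account.** In favour: allocation follows consent, both materials are absorbable, the staples are described as lying under the skin, and wound care is similar. Section 2 mentions a removal visit only for steel staples, which neither arm uses. Not settled: the Monocryl closure is never described as subcuticular, and the documents do not say whether women are awake at closure or could tell the closures apart by sight or feel. Partial masking is plausible; complete masking cannot be assumed.

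**The case against.** The strongest case on the other side is that an open-label comparison of surgical closures, with cosmesis rated blind, is a defensible design. The primary outcome is operating-room time, the stated objective is operative time and wound cosmetics, and only secondary outcomes are exposed. That stands, and it limits how much weight this point carries.

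The practical objections also stand in part. Section 6.2 gives the randomization scheme to research staff, and section 6.3 has research staff or a trained provider collect outcomes, so those who administer the questionnaires may know the arm. Pain is a routine nursing question taken from the chart. Removing the closure from nursing hand-off or discharge papers would change routine documentation and could affect communication about a wound, so it is not part of the fix. Section 6.3 also allows outcomes to be obtained by phone after a missed visit, so masking should end when the questionnaires are complete, not on a fixed day.

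A reader might make four stronger inferences that the documents do not support:

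- *That women are told their closure.* No section says so. Open-label means that masking is not planned; it does not establish disclosure, and the consent pages are not available to check.
- *That the trial is wholly unmasked.* The photograph rating is blinded.
- *That both closures are known to lie under the skin.* This is explicit for the staples only. For Monocryl it is a plausible inference.
- *That the calculated probabilities estimate the actual bias.* They show what an assumed shift would do. If women hold no expectation, the bias is zero.

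**Conclusion.** The point holds for the secondary outcomes. The plan combines subjective, self-reported outcomes, a listed direction of benefit on two of them, and neither participant masking nor a reason for its absence. The primary outcome is not reached through the woman's knowledge, and 316/352 and 90% power are unchanged.

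The size is unknown. Under an assumed SD of 2.0 to 2.5 and 158 evaluable women per arm, a 0.3-point shift would raise the chance of a nominally significant pain difference from 0.05 to about 0.19-0.27. That range rests on the assumed SD and shift, on no true effect, and on the evaluable number for operating-room time applying to the questionnaires as well. How much of such a bias partial masking would remove cannot be estimated from the documents. The case for acting is that the change is cheap and that awareness of the allocation cannot be undone once the data are collected.

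**What to change.** - **Section 3.** Replace *open-label* with: *surgeon open; participants not told their allocation by study staff, where feasible, until their POD 5-10 questionnaires (including any completed by phone) are done*. Say the same in the consent form.
- **Clinical care.** Leave clinical records, and clinicians' disclosure to the patient, unchanged.
- **Wound-check questionnaire.** Add one closing item asking which closure the woman thinks she had, and report the answers by arm.
- **Reporting.** Describe Bluebelle, pain and satisfaction as at best partially masked.

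The cost is a change of wording in the protocol and consent form, an instruction to study staff and one questionnaire item. No extra visits or staff are needed, and the sample size and power stay the same. The downside is that masking will be incomplete: some women may hear, infer or be told the device, and staff collecting outcomes may know the arm. The arm-guess item helps to show how far the masking held.

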6.2 Randomization

A confidential computer-generated simple randomization scheme will be prepared and provided on an ongoing basis to our research staff. A randomization log with group assignment, patient name and medical record number will be used to track the randomization process.

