6.6. Primary Outcome

OR Case time in minutes

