8.3. Loss of Confidentiality

Any time information is collected there is a potential risk for loss of confidentiality. Every effort will be made to keep patient's information confidential; however, this cannot be guaranteed.

9. Subject Safety and Data Monitoring

The PI and research staff will be responsible for monitoring the safety of this study. A report to the IRB will be submitted according to its policy if adverse events (AEs) or serious adverse events (SAEs) occur, and any changes in the protocol as a result of these events. No interim analysis will be planned and there will be no study-specific criteria to halt the study. Since, Monocryl and INSORB absorbable stables are deemed safe and available for use according to the FDA, there are no safety and minimal toxicity concern.

The research staff will ensure all aspects of data quality including monitoring for adherence to consent procedures, inclusion and exclusion criteria, valid abstraction, correct entry, timeliness and responsiveness to data queries.

Data collection will take the form of excel data entry and will be identified with a participant ID number. Data will be collected and stored with the participant ID code only. The master enrollment log linking patient identifiers with study ID numbers will be kept in a password-protected database on the Ob/Gyn Department's internal server separate from the data. Several data collection forms will be used. Data on these forms devoid of personal identifiers will be securely stored at our perinatal research division. The research staff will be available to monitor the data and correct any discrepancies based on source documents if needed. The principal investigator and research staff will monitor the study accrual rate, study attrition including withdrawals/dropouts, and any changes in risk/benefit bi-annually.

Each subject will be provided contact information to reach study staff. Additionally, the consent form provides instructions and a mechanism of contact for subjects to reach the primary investigator and also provides contact information for the subject to contact the IRB directly. Any significant concerns or complaints or requests for study information would be directed from the study staff to the study coordinator and study PI. Any complaints or adverse events gleaned from these contacts would be reported to the IRB (per IRB policy) and to the sponsor.

10. Procedures to Maintain Confidentiality

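### The randomization scheme goes to the staff group that screens and consents, and no step conceals the next assignment until eligibility is fixed at skin closure, when elapsed operating time is already visible

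*Combined protocol and SAP*

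**What the plan says.** Section 6.2 consists of two sentences. The first is "A confidential computer-generated simple randomization scheme will be prepared and provided on an ongoing basis to our research staff". The second describes a record of assignments: "A randomization log with group assignment, patient name and medical record number will be used to track the randomization process".

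The research staff have other duties at entry to the trial. Section 6.1 says that "trained research staff will be available 24/7 to screen and consent subjects" and, under the consenting process, "The research staff will be responsible for the informed consent". Section 9 gives them general oversight of data quality, including "monitoring for adherence to consent procedures, inclusion and exclusion criteria".

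On timing, Section 6.1 says "Women will be randomized in the operating room when the decision is made to proceed with skin closure and they continue to be eligible". It does not say who makes that final eligibility check. Among the exclusions in Section 5 is a judgement about further surgery: "High likelihood of additional surgical procedure beyond planned cesarean".

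The primary outcome is "OR Case time in minutes", with no start or stop point given. Section 3 describes the trial as open-label. No section mentions sealed envelopes, central or web-based release, a holder of the list who is independent of recruitment, or a rule that eligibility is locked before the assignment is seen.

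**The concern.** Concealment matters at the moment when someone decides whether a woman enters. Here that moment comes late. Skin closure is near the end of a cesarean, so those present know whether the case has run long or short. In most trials, foreknowledge of the next assignment works through a prognostic factor that is only loosely tied to the outcome. In this trial it could work on part of the outcome itself.

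The route is narrow but exists. The additional-procedure exclusion calls for judgement and is naturally related to duration. If the next assignment were visible, a long case could be judged no longer eligible when one arm was next and accepted when the other was. The unused assignment would pass to the next woman, and the group sizes would show nothing. Analysis by intention to treat gives no protection, because a withheld woman is never randomized. The screening log covers women approached, but nothing requires a reason or a time for a consented woman who is not randomized, so the pattern would be hard to detect.

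The target difference is small relative to the outcome: 5/55.46 = 9.0% of the control mean. A modest amount of selection is therefore not negligible.

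**Working it through.** **The plan's own figure.** Section 12 gives a control SD of 13.63 min, a difference of 5 min, two-sided alpha 0.05 and 90% power. Then d = 5/13.63 = 0.3668. With 158 per arm, the noncentrality is 0.3668 × √(158/2) = 3.2605, the critical t is 1.9675 on 314 df, and the power is 0.9016. This matches the printed output (316 in total). Allowing for 10% loss, 316/0.9 = 351.1, which becomes 352, or 176 per arm. The sample size is not in dispute.

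**Illustration of the bias.** The documents give no figures for selective entry, so the following values are assumed: a fraction p of would-be entrants is withheld from one arm only; their mean time exceeds that arm's mean by x; there is no true effect; and 176 per arm are analysed.

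- Bias: b = p·x/(1 − p)
- Standard error: SE = 13.63 × √(2/176) = 1.453 min
- Two-sided type I error: Φ(b/SE − 1.96) + Φ(−b/SE − 1.96)

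| p | x (min) | b (min) | b as share of 5 min | b/SE | Type I error |
|---|---|---|---|---|---|
| 2% | 13.63 (1 SD) | 0.28 | 6% | 0.19 | 5.4% |
| 2% | 27.26 (2 SD) | 0.56 | 11% | 0.38 | 6.7% |
| 5% | 13.63 (1 SD) | 0.72 | 14% | 0.49 | 7.8% |
| 5% | 27.26 (2 SD) | 1.43 | 29% | 0.99 | 16.7% |

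In numbers of women, 2% is 176 × 0.02/0.98 = 3.6 withheld and 5% is 176 × 0.05/0.95 = 9.3. With 158 per arm, SE = 1.533 min, the biases are the same and the type I error runs from 5.4% to 15.5%.

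**A second model.** Suppose instead that the women with the longest elapsed time are dropped from one arm, total time is normal with SD 13.63, and elapsed time correlates 0.7 to 1.0 with total time (158 per arm). Dropping 2% gives 0.47 to 0.67 min and a type I error of 6.1% to 7.4%. Dropping 5% gives 1.04 to 1.48 min and 10.6% to 17.4%. The two models agree in order of magnitude.

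**Can analysis recover it?** Under the second model (correlation 0.9, longest 5% dropped, 176 per arm, no true effect), simulation gives an unadjusted type I error of about 0.16. Adjusting for elapsed time at randomization returns it to about 0.05, with a mean estimate near zero. This works because elapsed time is fixed before randomization. It would not remove selection on something unrecorded.

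**The case against.** The strongest reply is that the text is silent on the mechanism and does not describe an exposed list. The scheme is called confidential, and providing it continually is compatible with handing over one concealed assignment at a time. Simple randomization cannot be predicted from the log of past assignments, so foreknowledge would need sight of the list. A long case is not an exclusion. The woman has already consented, and closure is imminent, so she cannot be held back for a later assignment. Randomizing this late also leaves less room for dropouts after randomization. Logs of women approached and of women randomized already exist.

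Much of this stands, and it rules out three stronger readings that a reader might infer.

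- That staff do see upcoming assignments. The documents do not say so.
- That the person holding the scheme also confirms eligibility at skin closure. Section 6.1 names nobody, and Section 9 gives research staff only general oversight of the criteria.
- That any resulting bias would be beyond repair. Selection on elapsed time could be largely removed by adjusting for it.

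That most of the outcome has elapsed by skin closure is also an inference. It is a reasonable one, but the protocol neither defines case time nor divides it.

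The reply does not dispose of the point. Calling a scheme confidential is not a procedure, and the only recipients named are the group that recruits. If concealed release is intended, one sentence would say so. If it is not, the analysts cannot supply it later.

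**Conclusion.** The concern holds as a weakness in trial conduct that should be corrected; it is not evidence that bias has occurred. Three facts rest on the text: the scheme goes to the group that screens and consents, no concealing step is described, and entry is decided again in the operating room in an open-label trial whose primary outcome is operating time.

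The size is illustrative. Over the assumed range the effect runs from almost nothing (about a quarter of a minute, type I error close to nominal) to about 29% of the target difference with more than three times the nominal error. The upper end needs about nine long cases, each averaging 2 SD above the mean, all withheld from the same arm. Nothing in the documents makes that likely, and nothing in the described procedure prevents it.

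**What to change.** In Section 6.2, state that someone outside recruitment generates and holds the list. Assignments should be released one at a time, through a database randomization module or sequentially numbered opaque sealed envelopes, and only after a named role has recorded continued eligibility with a time stamp in the operating room.

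Extend the existing screening and randomization logs to record every consented woman who is not randomized, with the reason and the time.

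In Section 12, add a supporting analysis that either adjusts for time elapsed at randomization or takes time from randomization to the end of closure as the outcome. The randomization time stamp makes both possible. The start and stop of OR case time should be defined at the same point.

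The cost is protocol wording, minor set-up and a few seconds in the operating room. The sample size is unchanged. The concealment step has to be in place before the first woman is randomized.
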